As with any immune modulating agent, risankizumab has the potential to impair immune function resulting in a risk of infection. This will be addressed by clinical monitoring for adverse events (AEs) during the treatment and follow up periods. Subjects with positive screening for M. Tuberculosis (TB) (skin/interferon-gamma release assay [IGRA] test positive) will be further worked up for signs and symptoms of active TB (e.g., chest x-ray [CXR]). Subjects with active TB will be excluded from enrolling in the study. Subjects with latent TB will be allowed to enroll in line with local guidelines. If latent TB is established, TB prophylaxis/treatment should be initiated and maintained according to

local country guidelines. Subjects with current signs or symptoms of infection or history of serious infection will not be included in the study.

The role of IL-23 in tumor immunity is not well established at this time, but an increased risk of cancer from an IL-23 antagonist, though considered small, cannot be excluded.

Although rare, a potential for drug-induced liver injury (DILI) is under constant surveillance by sponsors and regulators. Therefore, though there is no known DILI risk with risankizumab, this study requires timely detection, evaluation, and follow-up of laboratory alterations of selected liver laboratory parameters to ensure subjects' safety.

An independent Data Monitoring Committee (DMC) will be assessing all potential safety signals and will be unblinded to treatment allocation. The DMC will review unblinded safety data on a cohort level, at a minimum of 6-month intervals throughout the course of the study. At the timing of this amendment, the DMC has provided recommendation that the study may continue without modification and allowed enrollment to begin for 16 - 17 year-olds. A patient information card with information of the symptoms and signs of hypersensitivity reactions, infusion related reactions as well as late stage reactions will be provided to the patients at Screening so that any such events once occurred will be reported immediately by the patients to the investigator.

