 - QuantiFERON[®]-TB test or Purified Protein Derivative (PPD) skin test, or both, according to local guidelines, will be performed during Screening. QuantiFERON[®]-TB test is preferred for subjects who received Bacillus Calmette-Guérin (BCG) vaccination or were exposed to other Mycobacteria species. Subjects with a positive test result (or indeterminate results that have been repeated) may participate in the study if further work up (according to local practice/guidelines) establishes conclusively that the subject has no evidence of active tuberculosis. Subjects with a history of active TB who have documented completion of a full course of anti-TB therapy may be allowed to enter the study after consultation with the AbbVie TA MD. If latent TB is established, TB prophylaxis/treatment should be initiated and maintained according to local country guidelines.
 - Have active hepatitis B or hepatitis C defined as:
 - HBV: hepatitis B surface antigen (HBs Ag) positive (+), or detected sensitivity on the HBV deoxyribonucleic acid (DNA) polymerase chain reaction (PCR) qualitative test for hepatitis B core antibody (HBc Ab) positive subjects;
 - HCV: HCV ribonucleic acid (RNA) detectable in any subject with positive anti-HCV antibody (HCV Ab)

24. Subject with a previous history of dysplasia of the gastrointestinal tract or found to have dysplasia, other than completely removed low-grade dysplastic lesions, in any biopsy performed during the Screening endoscopy.
25. Subject with a known history of lymphoproliferative disease, including lymphoma, or signs and symptoms suggestive of possible lymphoproliferative disease, such as lymphadenopathy and/or splenomegaly.
26. Subject with current or previous history of malignancy other than a successfully treated non-metastatic cutaneous squamous cell or basal cell carcinoma or localized carcinoma in situ of the cervix.
27. Subject who has severe, progressive, or uncontrolled renal, hepatic, hematological, endocrine, disorder or symptoms thereof.
28. Female subjects who is pregnant, breastfeeding, or is considering becoming pregnant during the study or for approximately 140 days after the last dose of study drug.
29. Subject who has any condition, including any physical, psychological, or psychiatric condition, which in the opinion of the Investigator, would compromise the safety of the subject or the quality of the data and renders the subject an unsuitable candidate for the study.

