Information on prior biologic, corticosteroid, immunomodulators (i.e., AZA, 6-MP, MTX), CD-related antibiotics, aminosalicylate or any other physician prescribed therapy for CD use will be obtained as outlined in Section 5.2.3.1.

A detailed medical history with respect to TB exposure will be documented. This information will include BCG vaccination, cohabitation with individuals who have had TB, and residence or work in TB endemic locations. Subjects with active TB (during Screening) or documented history of active TB who have documented completion of a full course of anti-TB therapy may be allowed to enter the study after consultation with the AbbVie TA MD. TB history and anti-TB therapy needs to be documented in the source documents and eCRFs.

Physical Examination

A physical examination including evaluation of extra intestinal manifestations (EIMs) will be performed at the designated study visits as specified in [Appendix C](#).

A full physical examination will be performed as outlined in [Appendix C](#). Physical examinations at all other visits (including unscheduled visits) are symptom based and should include the assessment of EIMs as part of calculating the Crohn's disease activity index (CDAI). The number of cutaneous fistulas should be recorded, including the number of fistulas draining upon gentle compression. Fistulas will be classified as abdominal or perianal/anal. Physical exam abnormalities noted by the Investigator at Baseline (including fistulas and fissures) will be recorded in the subject's medical history.

Abnormalities noted after the Baseline visit will be evaluated and documented by the Investigator as to whether they are AEs.

Additionally, physical examination findings that are related to or part of each subject's medical history will be captured on the appropriate medical history eCRFs.

Vital Signs

Vital sign determinations of systolic and diastolic blood pressure in sitting position, pulse rate, respiratory rate, and body temperature will be obtained at each visit. Blood pressure, pulse rate, and respiratory rate should be measured before blood draws are performed.

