If PPD and/or the QuantiFERON[®]-TB Gold test (or IGRA equivalent) is positive, or if there is a repeat indeterminate (note: the first indeterminate results must be repeated) QuantiFERON[®]-TB Gold test (or IGRA equivalent) upon retesting, subjects may participate in the study if further work up (according to local practice/guidelines) establishes conclusively that the patient has no evidence of active tuberculosis. Subjects with a history of active TB who have documented completion of a full course of anti-TB therapy may be allowed to enter the study after consultation with the AbbVie TA MD. If active TB is diagnosed, the subject may not enroll in the study. If presence of latent tuberculosis is established, then tuberculosis prophylaxis should be initiated and maintained according to local country guidelines. It is also necessary to report the latent TB or positive TB testing in the source documents and eCRFs.

- QuantiFERON[®]-TB Gold Test is the preferred method which will be analyzed by the central laboratory (QuantiFERON test is preferred over TB Skin Test). However, if other IGRA equivalent tests are used, these may be performed by a certified local laboratory at the Investigator's discretion.
- If the QuantiFERON[®]-TB Gold Test is NOT possible (or if both the QuantiFERON[®]-TB Gold Test and the PPD Skin Test are required per local guidelines) the PPD Skin Test will be performed according to standard clinical practice.
 - The PPD Skin Test should be read by a licensed healthcare professional between 48 and 72 hours after administration. A subject who does not return within 72 hours will need to be rescheduled for another skin test.
 - The reaction will be measured in millimeters (mm) of induration and induration ≥ 5 mm is considered a positive reaction. The absence of induration will be recorded as "0 mm" not "negative."
- If PPD and/or the QuantiFERON[®]-TB Gold test (or IGRA equivalent) is positive, or if there is a repeat indeterminate QuantiFERON[®]-TB Gold test (or IGRA equivalent) upon retesting, subjects may continue in the study if further work up (according to local practice/guidelines) establishes conclusively that the subject has no evidence of active tuberculosis.
- If presence of latent tuberculosis is established, TB prophylaxis/treatment should be initiated and maintained according to local country guidelines.

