- A microscopic analysis will be performed by the central laboratory in the event the dipstick results show leukocytes, nitrite, protein, ketones, or blood greater than negative or glucose greater than normal.
- INR test only drawn if ALT or AST > 3 × ULN (upper limit of normal) and Total Bilirubin ≤ 2 × ULN (Refer to Section 5.4.1, for additional information).
- Only done at screening and calculated by the central laboratory.
- To be done with the occurrence of a suspected anaphylactic reaction (an additional sample of tryptase to be collected if possible at least 2 weeks post-reaction or at the next study visit); for ADA these samples are collected in addition to those specified in Appendix C.

Hepatitis B Testing

All subjects will be tested for the presence of the HBV at Screening. A positive result for the Hepatitis B surface antigen (HBs Ag) will be exclusionary. Samples that are negative for HBs Ag will be tested for surface antibodies (HBs Ab) and core antibodies (HBc Ab Total). Subjects with HBs Ag (-), HBs Ab (-), and HBc Ab Total (+) require PCR qualitative testing for HBV DNA. Any HBV DNA PCR result that meets or exceeds detection sensitivity will be exclusionary.

Subjects with a negative HBs Ag test and tests showing the results below do not require HBV DNA PCR qualitative testing:

- HBc Ab Total (-) and HBs Ab (-)
- HBc Ab Total (-) and HBs Ab (+)
- HBc Ab Total (+) and HBs Ab (+)

For Japan only: for subjects with HBs Ab (+) and/or HBc Ab (+) at Screening, the HBV-DNA PCR test should be performed as outlined in [Appendix C](#). In cases where the recurrence of HBV-DNA is observed, the subject should be discontinued from the study drug. Retesting according to [Appendix C](#) is not necessary with subjects who have a history of HBV vaccine and are HBs Ab (+).

Hepatitis C Testing

All subjects will be tested for the presence of the hepatitis C Virus (HCV) antibody at Screening. Subjects with positive HCV antibody will have a HCV RNA test. If the HCV RNA is positive then the subject will be excluded.

HIV

Subjects with a known history of HIV infection are excluded from study participation. HIV testing will be conducted as part of the infection screening at the Screening visit. The Investigator must discuss any local reporting requirements to local health agencies with the subject. The site will report these results to their health agency per local

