- c. Subjects will be contacted 140 days following last dose of study drug for an assessment of any new or ongoing AEs, except those subjects who roll-over into Study M16-000 after the end of study participation.
- d. Update inclusion/exclusion, prior and concomitant therapy, and medical/surgical history information to assure subject eligibility.
- e. Physical examinations are full physical examinations at Screening and Week 12 and Week 24 if the subject receives treatment in Induction Period 2. Physical examinations at all other visits (including unscheduled visits) are symptom based and should include the assessment of EIMs and a count of the number of cutaneous fistulas as part of calculating the CD4I.
- f. Blood pressure, pulse rate, temperature, respiratory rate and weight should be performed before blood draws are performed. Height will be measured at Screening only (with shoes off and then adding 1 inch or 2.5 cm) for subjects \geq 18 years of age. Height will be re-measured at Week 12 and Week 24 (if applicable) for subjects $<$ 18 years of age at Baseline.
- g. Collection of SAEs and protocol-related nonserious AEs begins the day the subject signs the informed consent.
- h. Subjects with negative QuantiFERON-TB Gold test and/or PPD test within 90 days of Screening will not require a repeat test (documentation must be available). PPD skin test is to be read 48 to 72 hours after placement. In case of positive PPD/positive or repeat indeterminate IGRA testing, subjects may participate in the study if further work up (according to local practice/guidelines) is negative for active TB.
- i. For subjects with a normal ECG taken within 90 days of Screening, a repeat ECG at Screening will not be required, provided source documentation is available. Subjects can have a repeat ECG at any time during the study as warranted based on the opinion of the Investigator.
- j. Subjects will be tested for the presence of the HBV and HCV at Screening. A positive result for the hepatitis B surface antigen (HBs Ag) or hepatitis C (HCV RNA detectable in any subject with anti-HCV Ab) will be exclusionary. For subjects who are negative for HBs Ag but are positive for core antibodies (HBc Ab), HBV DNA PCR will be performed and any result that meets or exceeds detection sensitivity will be exclusionary.

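### Section 5.3.1.1 waives HBV DNA PCR for surface-antigen-negative subjects positive for both core and surface antibody, while Appendix C note j requires it; two smaller TB and serious-infection mismatches need the same clean-up

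*Protocol*

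**What the plan says.** **Hepatitis B.** The Hepatitis B Testing text in Section 5.3.1.1 defines who needs the PCR: "Subjects with HBs Ag (-), HBs Ab (-), and HBc Ab Total (+) require PCR qualitative testing for HBV DNA". It then states: "Subjects with a negative HBs Ag test and tests showing the results below do not require HBV DNA PCR qualitative testing". Three patterns follow, and the third is positive for both core and surface antibody. Appendix C, note j, sets a different trigger: "For subjects who are negative for HBs Ag but are positive for core antibodies (HBc Ab), HBV DNA PCR will be performed". It adds that a result at or above detection sensitivity excludes the subject. Exclusion criterion 23 in Section 5.2.2 counts as active hepatitis B a "detected sensitivity on the HBV deoxyribonucleic acid (DNA) polymerase chain reaction (PCR) qualitative test for hepatitis B core antibody (HBc Ab) positive subjects".

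**Tuberculosis.** The Medical and Surgical History text in Section 5.3.1.1 names "Subjects with active TB (during Screening) or documented history of active TB who have documented completion of a full course of anti-TB" therapy as people who may be admitted after consultation with the sponsor's medical director. The TB Testing text in the same section says: "If active TB is diagnosed, the subject may not enroll in the study". Section 3.2 likewise says that subjects with active TB are kept out.

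**Serious infection.** Section 3.2 says: "Subjects with current signs or symptoms of infection or history of serious infection will not be included in the study". Section 5.2.2 lists no exclusion for a history of serious infection, and criterion 23 lets in subjects with fully treated past active TB after consultation.

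**The concern.** The hepatitis B check is a safety screen for a drug that Section 3.2 itself says could impair immune function and lead to infection. If two parts of one protocol set different triggers for the same test, a subject can pass screening under one part and never reach the test that would have excluded that subject under the other. Section 7.0 does not allow intentional deviations, so whoever follows one rule departs from the other. The TB and serious-infection wording raises a similar question on a smaller scale: does the safeguard described in the benefit-risk section match what sites are told to apply?

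**Working it through.** No sample-size, power or error-rate figure is involved, so the check is a comparison of the rules in the current protocol (synopsis dated 01 September 2020), not of its amendment log.

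**Step 1. PCR duty by serology, among HBs Ag-negative subjects.**

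| HBc Ab | HBs Ab | Section 5.3.1.1 | Appendix C note j | Agree? |
|---|---|---|---|---|
| − | − | no PCR | not called for | yes |
| − | + | no PCR | not called for | yes |
| + | − | PCR | PCR | yes |
| + | + | no PCR | PCR | **no** |

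The conflict sits in one of the four patterns.

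**Step 2. Effect on eligibility in that pattern.**
- HBV DNA undetectable: the hepatitis B rule keeps nobody out under either text. Only the test differs.
- HBV DNA detectable: under Section 5.3.1.1 no PCR is done, so nothing triggers exclusion and the subject enters if otherwise eligible. Under note j the PCR is done and the subject is excluded.

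**Step 3. Does other text settle it?**
- Table 1 lists the HBV DNA PCR as a reflex test but gives no trigger.
- Criterion 23 says what follows from a detected PCR in a core-antibody-positive subject. It does not say who must be tested.
- The Japan-only provisions apply to Japan. Note k there speaks of repeating the PCR at Weeks 12 and 24, which presupposes a Screening PCR but does not settle the rule elsewhere.

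Nothing resolves the conflict.

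**Step 4. Tuberculosis.**
- Active TB at Screening: possibly admissible under the medical-history text (completed therapy, consultation); barred without exception under the TB Testing text and Section 3.2. These do not match.
- Past active TB, fully treated: possibly admissible under criterion 23, the medical-history text and the TB Testing text. It is barred by Section 3.2 only if active TB counts as a serious infection, which the protocol does not say.
- Latent TB: allowed, with prophylaxis or treatment under local guidelines, in Section 3.2, criterion 23 and TB Testing. These agree.
- Appendix C note h: participation after a positive or repeat indeterminate test requires a work-up negative for active TB. This agrees with criterion 23 and TB Testing.

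**Step 5. Serious infection.** The nearest criteria in Section 5.2.2 are the first bullet of criterion 23 (active, chronic or recurrent infection that the investigator judges makes the subject unsuitable) and criterion 29 (any condition that the investigator thinks compromises safety or data quality). Both rest on judgement, and neither names a past, resolved serious infection. Section 3.2 states the bar flatly.

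**The case against.** Much can be said for a narrower view, and most of it stands.

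A reader might infer that criterion 23 and Section 3.2 also contradict the hepatitis B rule. They do not. Criterion 23 gives the consequence of a detected PCR, and Section 5.3.1.1 gives the same consequence. Section 3.2 does not mention hepatitis B. The conflict is between Section 5.3.1.1 and note j alone.

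A reader might also infer that about 400 sites will apply different rules. The documents do not show this. Clinical laboratory tests go to a certified central laboratory, and a centrally triggered reflex would normally follow one algorithm. That algorithm is not shown, however, and the protocol gives two specifications for it, so the objection limits the consequence without removing the contradiction.

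On TB, the completed-therapy condition in the medical-history sentence can be read as covering both groups it names, and entry is discretionary. Re-screening is allowed with no minimum wait, so a subject found to have active TB could be treated and return later. That reading is fair and makes this limb the weaker one. It does not clear it: a subject who returns after treatment has a history of active TB, which the sentence already covers separately, and the bars in TB Testing and Section 3.2 carry no exception.

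On serious infection, it would go too far to say that no criterion enforces the safeguard. The first bullet of criterion 23 and criterion 29 let an investigator exclude on infection grounds. What remains is a flat statement in Section 3.2 with no explicit counterpart in Section 5.2.2.

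**Conclusion.** The hepatitis B contradiction is real and unresolved in the current text. It is confined to HBs Ag-negative subjects positive for both core and surface antibody. For all of them the duty to test conflicts; for those with detectable HBV DNA, eligibility conflicts too. It would be wrong to say that eligibility is in doubt for every subject with that pattern. The documents give no serology frequencies, so no count can be offered.

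The TB sentence is a smaller conflict, softened by its completed-therapy condition and by the consultation requirement. It does not support saying that any subject with active TB at Screening may enter. The serious-infection statement is a mismatch between the benefit-risk narrative and the criteria. The further clash with the allowance for treated past TB depends on counting active TB as a serious infection.

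All three concern the consistency of eligibility and safety rules. None changes an endpoint, the significance level, the power or the sample size. The hepatitis B point should be corrected because a stated screening safeguard cannot be followed as written. No view is taken here on which clinical rule is right.

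**What to change.** The sponsor's medical and safety leads should:
1. Reconcile the Hepatitis B Testing text in Section 5.3.1.1 with Appendix C note j, so that one rule says who has the HBV DNA PCR at Screening.
2. Check the central laboratory's reflex specification against that rule and align it.
3. Reconcile the active-TB wording under Medical and Surgical History with TB Testing and Section 3.2.
4. Align the serious-infection statement in Section 3.2 with Section 5.2.2, including its treatment of past, fully treated active TB.
5. Notify sites.

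Appendix C note h needs no change. The cost is amendment wording, a check of the laboratory specification and a site letter. Depending on the rule chosen, there may be some added reflex PCRs in the one discordant pattern, which note j already foresees.

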***C. Difficile* Stool Testing**

During the Screening period a stool sample will be collected and sent to the central laboratory for testing. The sample will be assessed for the presence of *C. difficile* toxin.

The sample must be shipped to the central laboratory using dry ice. Additional information is available in the laboratory manual provided by the central laboratory.

Subjects who are positive for *C. difficile* toxin may be treated appropriately and re-screened.

Urinalysis

Dipstick urinalysis will be completed by the sites at all required visits as listed in [Appendix C](#). A microscopic urinalysis will only be performed by the central laboratory if the dipstick urinalysis results are abnormal, where abnormal is defined as leukocytes, nitrite, ketone, protein, blood or glucose value of greater than a trace.

Pregnancy Testing

A serum pregnancy test will be performed for all female subjects of childbearing potential during Screening.

The serum pregnancy test will be sent to and performed by the central laboratory. If the serum pregnancy test is positive the subject is considered a screen failure. If the serum pregnancy test is borderline, it should be repeated to determine eligibility ≥ 3 days later. If the repeat serum pregnancy test is:

- Positive, the subject is considered a screen failure;
- Negative, the subject can be enrolled into the study;
- Still borderline ≥ 3 days later, this will be considered documentation of continued lack of a positive result and the subject can be enrolled into the study (unless prohibited locally) in the absence of clinical suspicion of pregnancy and other pathological causes of borderline results.

A urine pregnancy test will be performed for all WOCBP as indicated in [Appendix C](#), prior to study drug administration. More frequent pregnancy tests will be performed throughout the study if required per local/country requirements.

- If the baseline urine pregnancy test performed at the site is negative, then dosing with study drug may begin. If the baseline urine pregnancy test performed at the site is positive, dosing with study drug must be withheld and a serum pregnancy test is required. The serum pregnancy test will be sent to and performed by the central laboratory. If the serum pregnancy test is negative, study drug may be started. If the serum pregnancy test is positive, study drug must be withheld and the subject must be discontinued from the study. In the event a pregnancy test result is borderline, a repeat test is required.
- If a urine pregnancy test post-baseline is positive, study drug will be temporarily discontinued and a serum pregnancy test is required. The serum pregnancy test will be sent to and performed by the central laboratory. If the serum pregnancy test is negative, study drug may be restarted. If the serum pregnancy test is positive, study drug will be permanently discontinued.

A pregnant or breastfeeding female will not be eligible for participation or continuation in this study or be allowed to continue study drug.

High-Sensitivity C-Reactive Protein (hs-CRP)

Blood samples for hs-CRP will be obtained per [Appendix C](#). The hs-CRP results will remain blinded to Investigator, study site personnel and the subject.

Blood draws should be performed, as much as possible, after all efficacy assessments, questionnaires (CDAI, IBDQ, etc.), and vital sign determinations are obtained and before study drug administration during a visit. In order to maintain the study blind, local laboratory testing for hs-CRP for routine subject monitoring should not be performed.

Crohn's Disease Activity Index (CDAI)

Average daily SF, average daily AP score, and well-being will be calculated from the subject diary. During screening subjects will be instructed on how to calculate the number of very soft and liquid stools, including a visual depiction. Physical exam and appropriate laboratory values will be calculated at all study visits beginning at Baseline. The Screening period will be a minimum of 7 days to calculate the Baseline scores.

The CDAI scores must be calculated using a central laboratory hematocrit (Hct) value from the same visit for all visits, except Baseline, where the most recent Screening Hct value will be used. The final CDAI for all other visits will be calculated once the hematocrit value is received from the central lab. If the Hct is missing due to technical issues (e.g., lost sample, clotted sample, etc.), the Hct value from the preceding visit may be used.

Instructions to calculate CDAI

- To answer **questions one (1) through three (3)**, entries from the 7 days prior to the visit should be used as recorded by the subject from the diary.
- Diary entries should not be included in the 7 days evaluated prior to the visit if: (1) the day the subject received medication for bowel preparation prior to endoscopy, (2) the day the subject underwent an endoscopy, and (3) 2 days following the endoscopy. Diary entries, up to 14 days prior to the visit, will be used accordingly in order to provide the most recent data for 7 days prior to the respective study visit. The 7 days do not need to be consecutive.
- In **question four (4)**, for the section regarding presence of anal fistulas and other fistulas, all fistulas detectable on physical examination (draining and

non-draining) should be captured on the CDAI and calculated into the CDAI score.

- And the evaluation for fever should include all the days that are taken into account for the calculation of the CDAI.
- When completing **question five (5)** ("Taking Lomotil/Imodium/Loperamide/opiates for diarrhea, 0 = no, 1 = yes") on the CDAI, "no" should be answered if a subject is taking an opiate(s) solely for pain. The use of these medications takes into account only the day of the scheduled visit and is only assessing their use as anti-diarrheals.
- For **question seven (7)**, hematocrit results from central laboratory will be used for the CDAI calculation. If the hematocrit value contains more than one decimal point, the rounding will be allowed to the tenths decimal (e.g., Hct value 33.44 will be captured as 33.4, Hct value of 33.45 will be captured as 33.5). The Hct values either prior to completing the calculation or at the subtotal box 7 of the CDAI should not be rounded to a whole number.
- For **question eight (8)**, the height obtained at Screening should be used when selecting the standard weight in [Appendix G](#), and this standard weight should be used for calculating every CDAI throughout subject participation in the study.
- Standard height is calculated by using the height obtained at Screening (without shoes) adding one inch or 2.5 cm. For subjects < 18 years of age at Baseline, height will be re-measured at Week 12 and Week 24 (if applicable) and standard height should be recalculated.
- If the body weight obtained at the time of assessment is not captured in kilograms (kg), then when converting into kg, rounding should occur using the second digit after the decimal (also known as the hundredth place) where if the number is 0 – 4, then keep the first digit after the decimal (also known as the tenth place) unchanged. If the second digit after the decimal is 5 – 9, then round up the first digit after the decimal (e.g., 90.246 would be captured as 90.2 and 97.687 would be captured as 97.7).
- The subtotal of box 8 should not be rounded to a whole number.

The calculation of the CDAI score is in [Appendix F](#).

Endoscopy

An endoscopy will be performed on the following visits:

- During Screening*
- Week 12/PD
- Week 24

The same endoscopist, where possible, should perform all endoscopies. In addition, where possible, the Investigator or sub-Investigator should be the endoscopist for the study. It is expected that all subjects who remain in the study through at least Weeks 8 will have a Week 12/PD endoscopy.

* An endoscopy performed before the Screening visit, independently of the study, may be used as the Screening endoscopy, with the approval of the AbbVie TA MD, if the following conditions are met:

1. Biopsy confirmation of the diagnosis is available according to section "Biopsy During Endoscopy" below, as applicable.
2. The endoscopy took place within 45 days prior to Baseline visit.
3. The endoscopy was recorded in a video format as the endoscopic eligibility will be determined by the central reviewers.

All ileocolonoscopies will be performed and recorded at the site in a video format. Sites should also perform the SES-CD assessment and record the findings on the SES-CD score sheet ([Appendix E](#)) and in the appropriate eCRF.

All endoscopies will be reviewed by a central reviewer who is blinded. Endoscopies completed at Week 12 and Week 24, for those subjects who undergo blinded therapy in Induction Period 2, will use the local reader results for stratification for Study M16-000.

There will be a window of ± 7 days to conduct the ileocolonoscopy. This window may be extended as necessary after consultation with the AbbVie TA MD in case of external circumstances.

The endoscopies performed at the time points described above will be used to provide the endoscopy subscores to calculate the SES-CD. All attempts should be made by the endoscopist to explore all segments of the colon and terminal ileum, including intubation of the terminal ileum, at every endoscopy visit. The endoscopy subscores by segment will be noted in the subject's source documents and in the database but the central reviewer's endoscopy subscore will be used for the efficacy analyses.

Biopsy During Endoscopy

Appropriate documentation of biopsy results consistent with the diagnosis of CD, in the assessment of the Investigator, must be available in order to confirm the subject's eligibility for the study. If this documentation is not available a diagnostic biopsy from the most affected area of the colon must be performed during the Screening endoscopy and read by a qualified local pathologist and the results reviewed by the Investigator. Biopsies to rule out dysplasia and colon cancer may be taken per the Investigator's discretion during any endoscopy performed during this study and evaluated by the local pathologist.

If any biopsy sample(s) are obtained, it should also be recorded on the video.

Any biopsy sample(s) will be collected from the respective bowel segment during the withdrawal of the endoscope and after sufficient recording for the central reader to calculate the SES-CD.

The signed pathology report will be monitored by the responsible CRA and kept with the subject's source documents onsite. Subjects should not be enrolled if high grade colonic dysplasia or colon cancer is discovered at Screening endoscopy or endoscopy performed within 45 days prior to Baseline visit. Subjects may be enrolled if low grade colonic dysplasia is discovered during endoscopy and is completely removed.

If a diagnosis of high grade colonic dysplasia or colon cancer is discovered during any subsequent endoscopic evaluation during the course of the study, the findings should be recorded as an AE and the subject should be discontinued from the study. If low grade colonic dysplasia is discovered during any subsequent endoscopic evaluation during the course of the study, the findings should be entered as an AE and the subject can continue in the study if the lesion has been completely removed.

Subject Diary

Subjects will be dispensed an electronic diary at Screening and will be trained on how to complete the diary by site staff during the Screening visit. All subjects should complete their subject diary on a daily basis throughout the entire study. The diary will be reviewed by site personnel with the subject at each visit and collected at the Final/PD visit, unless the subject continues into Study M16-000. Subjects should also be dispensed the patient information card at Screening.

Completion will be reinforced during study visits as necessary.

Outcomes and Questionnaires

Subjects will be asked to complete the following electronic questionnaires/outcomes at the time points indicated in [Appendix C](#).

- Inflammatory Bowel Disease Questionnaire (IBDQ)
- Work Productivity and Impairment Questionnaire – CD (WPAI-CD)
- Crohn's Symptom Severity (CSS)
- Patient Global Impression of Change (PGIC)
- Patient Global Impression of Severity (PGIS)
- Functional Assessment of Chronic Illness Therapy-Fatigue (FACIT-F)
- European Quality of Life 5 Dimensions (EQ-5D-5L)
- 36-Item Short Form Health Survey (SF-36)

Due to the COVID-19 pandemic and any local restrictions, sites may administer PRO instruments over the phone as needed. Sites may read the PRO questions and response options to the subject and record the subject's responses. Sites may send the questionnaires (email or hard copy) to the subjects to allow them to read/understand the questions and responses when the subject is providing responses over the phone. The date and time of PRO data collection should be recorded along with who collected the information.

Study Drug Dispensing/Administration

Intravenous and SC study drug will be administered to all subjects on-site. For WOCBP subjects, the urine pregnancy test needs to be negative prior to receiving study drug. The site will be provided administration instructions. Also, the initial 20 subjects enrolled between the Phase 3 induction trials will be monitored on site for 2 hours after completion of each infusion. Subjects should be observed after study drug administration until judged clinically stable by the study personnel. If an anaphylactic reaction or other serious allergic reaction occurs, administration of study drug should be discontinued immediately, appropriate laboratory testing samples drawn and appropriate therapy initiated.

Study drug kits are assigned by the IRT following the subjects randomized treatment schedule. (Refer to Section 5.5 for additional information).

During the Study Drug Dosing Period, a subject with confirmed (viral test positive) or suspected COVID-19 infection can only be dosed with study drug if the following COVID-19 viral clearance criteria are met:

- Symptomatic subjects: At least 2 negative viral tests in a row, ≥ 24 hours apart after at least 10 days have passed since recovery, defined as resolution of fever without use of antipyretics and improvement in respiratory symptoms (e.g., cough, shortness of breath)
- Asymptomatic subjects: At least 2 negative viral tests in a row, ≥ 24 hours apart after at least 10 days have passed since prior positive result (note:

subjects who develop symptoms will follow guidance above for symptomatic subjects)

